MAT treatment (treatment as usual) when combined with counseling has a decent success rate at greater than 50% patient retention over a 6-month period. Patients retained in MAT treatment typically experience substantial improvement in their opioid use, while those who discontinue MAT typically relapse to opioid use. Therefore it is important to try to improve the rate of retention in treatment, which is why the reSET-O intervention is proposed. Patients enrolling in the study will have been prescribed their appropriate MAT as their standard of care and is not part of the research study.

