8.3 Statistical methods

Outcome Measures and Covariates

Primary outcome: The primary outcome will be a binary indicator of whether or not the patient is retained on MAT (methadone, buprenorphine, or buprenorphine-naloxone) treatment through 24 weeks. For those who drop out before 24 weeks, time (week) of dropout will be recorded, and they will be considered as not retained.

Secondary outcomes: 1) weeks of treatment retention (time to drop-out 0-24 weeks, survival; number of weeks retained, continuous); 2) urine-confirmed abstinence from opioids in the last 4 weeks (longitudinal (weeks 4, 8, 12, and 24), binary); 3) Days using opioids in the last 4 weeks (longitudinal, continuous); 4) Days using other drugs/alcohol in last 4 weeks (longitudinal, continuous); 5) coping strategies (CSS mean score; longitudinal, continuous); 6) social functioning (EuroQol, SCS, global scores and subscales; longitudinal, continuous); 6) overall mental health symptoms (K10; longitudinal, continuous); 7) HIV risk behavior—days in past 30 of vaginal or anal sex without a condom (longitudinal, continuous); Any needle sharing in past 4 weeks (longitudinal, binary); 7) Treatment satisfaction at week 24 (IAFF; continuous); 8) Serious adverse events (binary).

Additional variables: *Covariates, primary and secondary analyses:* Stratification factors: 1) any intravenous drug use (binary); 2) treatment with methadone vs buprenorphine at Hub vs buprenorphine at Spoke (categorical). *Moderators:* 1) both stratification factors will be explored as moderators; 2) demographic characteristics (gender, age, ethnicity etc.); 3) prescription opioid use only vs any heroin or fentanyl use (binary); 4) other substance use at baseline (any cannabis, any stimulant, any heavy drinking days; binary); 5) Probable major depression at baseline (binary based on PHQ score); 6) history of prior treatment for opioid use versus first treatment episode (binary). *Mediators:* 1) social functioning (EuroQol; continuous); 2) social connectedness (SCS; continuous); 3) opioid craving (continuous); 4) coping (CSS; continuous); and 5) mental health symptoms (K10; continuous).

Intent to Treat, Dropouts, and Missing Data

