All analyses will be on the Intent-to-treat (ITT) sample, i.e., all randomized subjects (N=200) according to the treatment arm to which they were assigned. For the primary outcome, patients that dropped out before 24 weeks will be considered not retained. For the secondary outcome urine-confirmed abstinence, missing data (patients who cannot be located) will assumed to be opioid positive (not abstinent), a typical assumption which is reasonable based on the high rate of relapse among patients with OUD who discontinue medication treatment (Weiss et al., 2011; 2015; Hser et al., 2016; 2017). For other secondary outcomes, missing data will be treated as missing at random. Longitudinal mixed effects models do not require complete data to provide estimates of the outcome, and the estimates are considered valid under the assumption that the data are missing at random (Little & Rubin, 2002). We will additionally perform sensitivity analysis for the secondary outcomes to examine the influence on the outcomes of dropout and missing data by performing several imputation methods, for instance imputing missing weeks as all abstinent or all non-abstinent. Comparison of the inferences from assuming various models for the missingness provides a measure of the validity of the efficacy estimate from the initial model.

Significance Testing and Preliminary Analyses

All tests for main effects will be performed at two-sided significance level of 5%. Before performing specific analyses, we will examine the distribution of outcome measures and covariates and investigate for outliers. The distributions of continuous variables will be checked for normality, and transformed, if necessary. Distribution of demographic variables will be examined and described in terms of means, standard deviations, proportions and 95% confidence intervals. Covariates will be examined for association with treatment outcome. Covariates associated with treatment outcome will be adjusted for in models used to test study hypotheses.

Primary outcome

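### Days using opioids are analysed as missing at random without regard to MAT status, which the plan itself ties to opioid use, so losing contact with patients after they leave MAT can bias this outcome

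*Combined protocol and SAP*

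**What the plan says.** All of the following is in the combined protocol and SAP.

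- **Urine abstinence (8.3).** Missing results are scored as opioid positive. The stated reason is that this is "a typical assumption which is reasonable based on the high rate of relapse among patients with OUD who discontinue medication treatment".
- **Days using opioids (8.3).** This longitudinal secondary outcome falls under the next rule: "For other secondary outcomes, missing data will be treated as missing at random".
- **Model (8.3).** Secondary outcomes are modelled on treatment and the two stratification factors, with covariates added if they relate to outcome. MAT status during follow-up is not named.
- **MAT status and use (7.4.1).** Patients kept on MAT usually improve, "while those who discontinue MAT typically relapse to opioid use".
- **Data on leaving MAT (8.3).** "For those who drop out before 24 weeks, time (week) of dropout will be recorded, and they will be considered as not retained".
- **Sensitivity analysis (8.3).** The plan also promises sensitivity analyses covering the secondary outcomes. The approach is described as "performing several imputation methods, for instance imputing missing weeks as all abstinent or all non-abstinent".
- **Follow-up off treatment (7.2.1, 7.2.2).** Locator information is collected so that patients can be assessed after leaving treatment. There are check-in calls at weeks 16 and 20 and a wider window at week 24.

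**The concern.** Two adjacent rules make different assumptions about largely the same missing patients. For urine, a patient who cannot be found is assumed to be using. For days of use, that patient is assumed to resemble others with the same arm, strata and earlier reports. The plan's own argument is that opioid use depends on whether the patient is still on MAT. If visits are missed more often after leaving MAT, missingness depends on a variable that predicts the outcome, is recorded, and is left out of the analysis.

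Two things are at stake. Mean use can be understated in both arms. If off-MAT patients are harder to reach in one arm than in the other, the between-arm difference can be biased in either direction. The two opioid outcomes could then disagree merely because their missing-data rules differ.

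**Working it through.** **1. The plan's own figure.** Section 8.2: 40% vs 59.7% retained, 100 per arm, 80% power, two-sided 5%. The pooled two-proportion formula gives 100 per arm and power 0.8003. The odds ratio is (0.597/0.403)/(0.40/0.60) = 2.22. Both reproduce. These rates imply that 60% of TAU and 40.3% of app patients have left MAT by week 24.

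**2. Assumed inputs, not in the documents.** Use-days in the last 28: 3 on MAT, 16 off. Missing visits: 10% on MAT; a share f of 50% or 70% off MAT.

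**3. Closed form at week 24** (r = retention).

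True mean = 3r + 16(1−r). TAU: 1.20 + 9.60 = 10.80. App: 1.791 + 6.448 = 8.24. True difference **−2.56**.

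Observed mean = [0.9r·3 + (1−r)(1−f)·16] / [0.9r + (1−r)(1−f)].

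- TAU, f = 50%: (1.08 + 4.80)/0.66 = 8.91
- TAU, f = 70%: (1.08 + 2.88)/0.54 = 7.33
- App, f = 50%: (1.612 + 3.224)/0.7388 = 6.55
- App, f = 70%: (1.612 + 1.934)/0.6582 = 5.39

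App minus TAU: −2.36 (50% both), −1.95 (70% both), −0.79 (70% TAU, 50% app), −3.52 (50% TAU, 70% app).

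**4. Do earlier visits remove the bias?** The closed form ignores them, so a random-intercept mixed model with visit-by-arm terms was simulated (visits at weeks 4, 8, 12 and 24; exponential time to leaving MAT). Week-24 differences from separate runs:

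| Off-MAT visits missing, TAU / app | True | Missing at random | Using MAT status |
|---|---|---|---|
| 50% / 50% | −2.28; −2.28 | −2.22; −2.26 | −2.23; −2.37 |
| 60% / 60% | −2.36 | −2.17 | −2.25 |
| 70% / 70% | −2.22; −2.37 | −1.90; −1.86 | −2.29; −2.31 |
| 70% / 50% | −2.30; −2.62; −2.37 | −0.82; −0.96; −0.86 | −2.32; −2.59; −2.29 |
| 50% / 70% | −2.29 | −3.14 | −2.10 |

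With equal loss the error averages (0.06 + 0.02)/2 = 0.04 days at 50% and (0.32 + 0.51)/2 = 0.42 at 70%. With 70% vs 50% it is about 1.5 days toward no effect. With the loss reversed it is −3.14 + 2.29 = −0.85, exaggerating the effect. The TAU mean was understated by about 1.3 to 3.0 days.

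**5. Does it depend on the week-24 contrast?** No. In a model with only a treatment main effect and equal loss, a true −1.40 was estimated as −1.15 at 50% and −0.89 at 70%.

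**6. Do the planned extremes bracket the truth?** Score missing visits as 0 or 28 days, using the closed form. The missing share is 0.34 (TAU) or 0.2612 (app) at f = 50%, and 0.46 or 0.3418 at f = 70%.

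- 50% in both arms: 4.836 − 5.88 = −1.04, and (4.836 + 7.314) − (5.88 + 9.52) = −3.25. These bracket −2.56.
- 70% TAU, 50% app: 4.836 − 3.96 = +0.88, and (4.836 + 7.314) − (3.96 + 12.88) = −4.69. These bracket it but leave the sign open.
- 50% TAU, 70% app: 3.546 − 5.88 = −2.33, and (3.546 + 9.570) − (5.88 + 9.52) = −2.28. The true −2.56 lies outside.

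**The case against.** **A safeguard is already planned.** The same paragraph commits to imputation-based sensitivity analyses for the secondary outcomes, including a non-abstinent extreme, and to comparing the inferences. It would be wrong to infer that the plan ignores departures from missing at random. But the methods are only examples, non-abstinent is not converted into days, the main estimate is untouched, and step 6 shows that the extremes can miss the truth or leave the sign open.

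**Leaving treatment is not missing data.** A reader might infer that differing dropout from MAT biases the result by itself. It does not: follow-up off treatment is planned in both arms, and with equal loss of off-MAT visits the error is small to moderate. The large error needs unequal loss. That is plausible but not shown. Only the app arm has weekly support calls (with opt-out), week-12 re-enrolment, a paid interview and prizes for favourable urine screens (7.2.1, 7.2.2, 13.0).

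**The simulated model is not exactly the planned one.** Section 8.3 names no visit-by-arm term and mixes mixed-model and GEE language. Step 5 shows that the bias is not confined to the week-24 contrast.

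**Imputing with MAT status still assumes missing at random, given that status.** This stands. Suppose unlocated off-MAT patients use 22 days and located ones 16, with 70% vs 50% missing. TAU is 1.20 + 0.6(0.3·16 + 0.7·22) = 13.32, the app arm is 1.791 + 0.403(0.5·16 + 0.5·22) = 9.45, and the true difference is −3.87. Using MAT status gives −2.56; ignoring it gives about −0.79. The method is closer but not sufficient, so a delta shift is needed.

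**The recorded week of leaving MAT may be uncertain.** The plan names no data source for unlocatable patients and no rule for re-entry or transfer. This also stands, and the primary outcome needs the same information.

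**Conclusion.** The point holds for days using opioids. The main analysis sets aside a recorded variable that the plan itself treats as a driver of opioid use, and the planned sensitivity analysis narrows the gap without closing it. On the assumed values, the error in the week-24 difference is about 0 to 0.4 days with equal off-MAT loss of 50-70%. With 70% TAU vs 50% app, a true value of about −2.4 is estimated as about −0.9, and the bias changes sign if the loss is reversed. These sizes are illustrations: the documents give retention planning rates but no loss-to-follow-up or use-day figures.

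Three stronger readings are not supported:

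- The plan does not assert that every unlocatable patient has relapsed; it assumes positivity for urine scoring.
- The relapse argument concerns opioids, so it does not contradict missing at random for other drugs and alcohol.
- The plan does not rank its secondary outcomes, so opioid-use days cannot be called the main one.

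The primary retention analysis is unaffected. The change should be made, but the trial does not turn on it.

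**What to change.** In the missing-data part of Section 8.3:

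1. For days using opioids, multiply impute missing visits from a model with on/off-MAT status at that visit (from the recorded week of dropout), arm, strata, baseline and earlier use. Then fit the planned model to the imputed data. Do not enter MAT status as a covariate there: it arises after randomisation, and adjusting for it would remove part of the treatment effect.
2. Keep as sensitivity analyses the plain missing-at-random model and the planned extreme-case imputations, stated as 0 and 28 days.
3. Add a delta shift for missing off-MAT visits, over a pre-specified range and allowed to differ by arm, because located and unlocated off-MAT patients may differ.
4. State the source for the week of leaving MAT, and how re-entry and transfer are coded. Report visit completion by arm and MAT status.

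Applying the same imputation to other drug and alcohol days is optional.

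The cost is SAP wording, one extra analysis step and somewhat wider intervals. No new data are needed if the week of leaving MAT can be established for patients who are not located.

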8.2 Sample size determination

Previous studies of MAT treatment of OUD indicate substantial drop out rates--typically in the 40% to 50% range still retained in treatment at 24 weeks. Assuming 40% retention in the TAU treatment group, a sample size of 100 patients per treatment group (total N = 200) is selected to ensure sufficient power of 80% with a two-sided level of significance of 5% to be able to detect a difference of at least 19.7% between the TAU vs reSET-O + TAU treatment groups (i.e., 40% retained in TAU vs 59.7% retained in reSET-O + TAU). This difference of 19.7% is equivalent to an odds-ratio of 2.22 and would be clinically meaningful.

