Statistical Model: *Hypothesis: Adding reSET-O to TAU (reSET-O + TAU arm) will promote greater 24 week retention in treatment on buprenorphine compared to the TAU arm.* The positive effect of randomization to the reSET-O+TAU group compared to TAU group will be estimated using logistic regression with the binary outcome of retention in treatment for 24 weeks (yes/no) modeled as a function of treatment condition (reSET-O + TAU vs TAU) and stratification factors (methadone treatment; buprenorphine treatment at Hub; buprenorphine treatment initiation at hub and continuation at spoke) and intravenous drug use in last 30 days (yes/no). The odds ratio of the treatment term and its confidence limits will estimate the treatment effect. The raw retention rates in each treatment group and rate differences will be computed for descriptive purposes.

Secondary outcomes

Statistical Models: For each of the secondary outcomes (see above) the effect of randomization to the reSET-O+TAU arm compared to the TAU arm will be estimated with a model of the same general form as for the primary outcome (three independent variables: treatment assignments (reSET-O+TAU vs TAU) and the two stratification factors) using logistic regression model (for binary outcomes), generalized linear model (for continuous outcomes), or longitudinal generalized mixed effects model (for longitudinal outcomes) with appropriate link functions (e.g. logit for binary outcomes). Longitudinal outcomes analyzed using a mixed effects models will utilize a generalized estimating equation with an autoregressive correlation structure to account for within subject correlation over time, as well a random intercept accounting for between subject variability. Retention data will be displayed with Kaplan-Meier curves that show the observed probability of retention in the program until time t, over time across the 24-week trial. The time to not-retained (dropout) data for reSET-O +TAU and TAU groups will be analyzed using proportional hazards models with covariates. If proportional hazard assumption is not satisfied, the data will be analyzed using a non-parametric log-rank test. In addition to stratification factors, covariates that are found to be related to the outcomes will be also added to the models to improve the power for detecting significant differences.

Moderation and Mediation

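### The plan names a primary logistic model but also adds covariates found to be related to the outcome, so the adjustment set of the primary odds ratio may be settled only after outcomes are seen

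*Combined protocol and SAP*

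**What the plan says.** All the relevant text is in Section 8.3, which Section 9.7 identifies as the detailed statistical analysis plan.

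- **Covariate list (Outcome Measures and Covariates).** For primary and secondary analyses it lists two stratification factors: any intravenous drug use, and methadone versus buprenorphine at Hub versus buprenorphine at Spoke. Moderators and mediators are listed separately.
- **Significance Testing and Preliminary Analyses.** "All tests for main effects will be performed at two-sided significance level of 5" percent. Covariates are then to be screened against the outcome, and "Covariates associated with treatment outcome will be adjusted for in models used to test study hypotheses". This paragraph comes just before the primary analysis and is not limited to secondary outcomes.
- **Primary outcome.** The comparison is labelled a hypothesis. Retention is "modeled as a function of treatment condition (reSET-O + TAU vs TAU) and stratification factors", these being the medication/site strata, together with intravenous use in the last 30 days. The odds ratio of the treatment term is the effect estimate.
- **Secondary outcomes.** The models have three independent variables: treatment and the two stratification factors. Beyond those factors, "covariates that are found to be related to the outcomes will be also added to the models", with the stated aim of improving power.

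Section 9.7 adds that the analysing statistician receives the data after data lock.

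**The concern.** A primary analysis should be fixed before anyone can see how covariates relate to the outcome. Here one paragraph gives a closed model and the paragraph before it gives a rule that can enlarge that model using the observed outcomes. The rule has no candidate pool, test, cut-off, pooling of arms or baseline-only condition, and nothing says which model governs if the two differ.

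The pool could be wide. Section 7.2 collects coping, social connectedness, psychological distress, recovery capital, trauma symptoms and overdose history, and several of these instruments are repeated after randomisation. Nothing says that post-baseline values would be used, and nothing excludes them.

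The scale of the estimate makes this matter more. A logistic odds ratio is non-collapsible: adding a prognostic covariate changes the quantity being estimated, even when arms are perfectly balanced. So the choice of covariates affects what the headline number means as well as its precision.

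**Working it through.** **Step 1: reproduce the plan's figure.** Inputs from Section 8.2: "Assuming 40% retention in the TAU treatment group", "40% retained in TAU vs 59.7% retained in reSET-O + TAU", and "sufficient power of 80% with a two-sided level of significance of 5" percent, with 100 per arm.

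Pooled proportion = (0.40 + 0.597)/2 = 0.4985.

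n per arm = [1.960·√(2·0.4985·0.5015) + 0.8416·√(0.40·0.60 + 0.597·0.403)]² / 0.197² = (1.3859 + 0.5835)² / 0.03881 ≈ 99.9, so 100. Power at 100 per arm is 80.03%.

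Odds ratio = (0.597/0.403)/(0.40/0.60) = 2.222, agreeing with "This difference of 19.7% is equivalent to an odds-ratio of 2.22".

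The sample size reproduces. It rests on raw proportions, so it does not depend on the covariate rule. The 2.22 is therefore an unadjusted odds ratio, whereas the analysis reports an adjusted one.

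**Step 2: compare the named model with a screened model by simulation.** The documents give no candidate covariates or strengths, so these are assumptions: 100 per arm; 10 or 20 standard-normal candidates; 3 prognostic at log-odds ratio 0, 0.3 or 0.6 per SD; screening with arms pooled at p < 0.05; conditional treatment odds ratio 1 or 2.22; 3,000 trials per row. The named model includes treatment, a three-level stratum and intravenous use (the last two given no effect here). Monte Carlo standard error is about √(0.05·0.95/3000) = 0.4 points at 5%, and 0.7-0.9 points for power.

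| Candidates | log-OR per SD | True OR | Rejects, named | Rejects, screened | Disagree | Median OR, named / screened |
|---|---|---|---|---|---|---|
| 10 | 0 | 1 | 5.1% | 5.1% | 0.8% | 1.00 / 1.00 |
| 10 | 0.3 | 1 | 4.7% | 4.8% | 2.0% | 1.00 / 1.00 |
| 10 | 0.6 | 1 | 4.8% | 4.5% | 4.3% | 1.00 / 0.99 |
| 20 | 0.3 | 1 | 5.2% | 5.3% | 2.6% | 1.00 / 1.00 |
| 10 | 0 | 2.22 | 80.5% | 79.9% | 1.9% | 2.29 / 2.30 |
| 10 | 0.3 | 2.22 | 75.5% | 75.4% | 6.3% | 2.15 / 2.23 |
| 10 | 0.6 | 2.22 | 62.9% | 70.8% | 13.2% | 1.95 / 2.30 |
| 20 | 0.3 | 2.22 | 76.0% | 74.4% | 6.6% | 2.17 / 2.25 |

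At a true odds ratio of 2.22, the 5th to 95th percentiles of the screened/named ratio of odds ratios were 0.95-1.07 with no prognostic covariates and 0.93-1.57 at log-odds ratio 0.6. The 62.9% is not evidence that N = 200 is too small: holding 2.22 as a conditional odds ratio shrinks the raw difference below the planned 19.7 points.

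**Step 3: vary covariate strength more finely.** With 12 candidates, 3 prognostic, p < 0.05, and assumed non-zero effects for stratum and intravenous use (2,000 trials per row, true odds ratio 2.22):

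| log-OR per SD | Disagree | OR, named / screened |
|---|---|---|
| 0 | 2.0% | 2.24 / 2.24 |
| 0.2 | 3.2% | 2.17 / 2.22 |
| 0.4 | 9.4% | 2.10 / 2.26 |
| 0.5 | 12.0% | 2.02 / 2.27 |

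A separate run of this setting gave a median of 2.01 versus 2.26 at the strong end, null rejection of 4-6%, and power of 72% for a fixed list of the prognostic covariates against 71% for screening.

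**The case against.** Four points on the other side deserve weight.

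1. *A model is named.* This stands. A reader might infer that the trial has no prespecified primary model at all. The documents do not support that: the primary paragraph specifies one in full, and the defect is that another paragraph leaves it open to additions.
2. *The covariate list is closed.* If the screening sentence refers only to the two listed stratification factors, nothing further enters the primary model. This reading is possible and makes the primary text ambiguous rather than plainly contradictory. It is weakened in two ways. The secondary paragraph adds covariates over and above the stratification factors, so the plan uses the word more widely. And the closed reading would make inclusion of those factors depend on observed association, whereas the primary model includes them unconditionally.
3. *Type I error is not at stake.* Largely right. One fixed screen on pooled arms kept rejection at 4.5-5.3% under the null. A reader might infer that the plan permits reporting the better of several models; taking the most favourable of the named model and four screening thresholds gave 6.0-7.6%. No passage permits that choice, so those figures describe a misuse rather than the plan.
4. *Adjustment is good practice.* Also right. The screened model had more power than the named one when covariates were strong, and its odds ratio lay nearer the simulated conditional value. A fixed list shifts the odds ratio in the same way, but its target is known in advance, and it matched screening on power.

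**Conclusion.** The concern holds as a conflict within Section 8.3 that should be resolved before data lock. For the secondary outcomes the outcome-driven rule is explicit. For the primary outcome the text is ambiguous, but its natural reach includes the primary hypothesis, and nothing says which model governs.

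The consequence is an odds ratio whose adjustment set, and therefore meaning, may be decided after outcomes are seen. It is not a demonstrated inflation of type I error. With 12 candidates, 3 of them prognostic at log-odds ratio 0 to 0.5 per SD, the two models reach different verdicts in about 2-12% of trials at an odds ratio of 2.22. The median odds ratio ranges from unchanged to 2.01 versus 2.26. Those sizes depend almost entirely on covariate strengths that the documents do not give. The textual finding is firm; the magnitude is illustrative.

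**What to change.** In Section 8.3:

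- Delete the outcome-driven covariate rule from both the preliminary-analyses paragraph and the secondary-outcomes paragraph.
- State that the primary odds ratio comes only from the model under Primary outcome. If more adjustment is wanted, add a short fixed list of baseline covariates already collected, named before data lock.
- Use one definition of intravenous use. The covariate list says any use, the primary model says the last 30 days, and Section 7.4.3 stratifies randomisation by medication/site only, so intravenous use should not be called a stratification factor unless it was one.
- Add the outcome's own baseline value, where collected, to each longitudinal secondary model, which at present holds only treatment and the two factors.
- Label any other adjusted model a sensitivity analysis.

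The cost is a wording change. The sponsor gives up the option of adding an unexpectedly prognostic covariate to the primary model. N = 200 and the stated 80% power are unchanged, and no new data are needed.

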7.2 Study Procedures

7.2.1 Visit 1 (Intake/Baseline)

During the subject's intake appointment, eligibility is confirmed by the provider and subjects are directed to a private research room. Research staff will introduce the research study to the participants and schedule a research appointment to discuss the project further in 7-21 days. Subjects can take a physical copy of the consent form home with them or request one be emailed to them.

During the first research appointment, research staff will confirm eligibility, complete the consent process, complete the baseline questionnaires, and randomize the subject (TAU + reSET-O or TAU alone). Participants will be asked to undergo research assessments consisting of an interview and self-report questionnaires (described below), as well as urine samples collected at all visits (baseline, week 4(+/- 2 weeks), week 8(+/- 2 weeks), week 12(+/- 2 weeks), and week 24(+2/- 4 weeks)). Urine toxicology for opioids and other drugs is collected at PPI as part of routine clinical care; however, urine collected at these specific clinic visits will also be used for

research purposes and used to confirm self-reports of abstinence. This will be outlined in the consent form and discussed with the participant.

Participants who are assigned to TAU + reSET-O will be briefed on the reSET-O app and will download the reSET-O app onto their smartphone or tablet device. Penn State research assistants will have the capability to generate and provide app access codes through the Pear Therapeutics clinician dashboard. This allows for instant access and entry into the app for the research subject, as opposed to waiting for several hours or even days for onboarding through the Patient Services Center. However, participants will still be required to complete the Pear Therapeutics reSET-O patient services center (PSC) enrollment form (completed with the research assistant), which will be transferred to the PSC via secure file transfer (e.g. Accellion or Kitedrive) or by fax. The PSC is affiliated with Pear Therapeutics, the owners of the reSET-O app. The following information is collected on the enrollment form and faxed to PSC:

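### Section 8.3 does not name the baseline value of any longitudinal secondary outcome as a model term; whether it enters is left to an unspecified selection on trial outcome data

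*Combined protocol and SAP*

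**What the plan says.** **Base model.** Section 8.3, Secondary outcomes, gives each secondary outcome a model with "three independent variables: treatment assignments (reSET-O+TAU vs TAU) and the two stratification factors". The covariates named for the primary and secondary analyses (8.3, Outcome Measures and Covariates) are those same two factors: intravenous drug use, and the methadone / buprenorphine-at-Hub / buprenorphine-at-Spoke category.

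**Additions.** The same Secondary outcomes paragraph continues: "In addition to stratification factors, covariates that are found to be related to the outcomes will be also added to the models", with the stated aim of improving power. Under Significance Testing and Preliminary Analyses, 8.3 gives a similar general rule for all hypothesis-testing models. Neither place lists candidates, a threshold or a selection method.

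**Baseline data.** Section 7.2.1 plans research assessments "as well as urine samples collected at all visits (baseline, week 4(+/- 2 weeks" and the later visits. It also lists the TLFB, CSS, SCS, PROMIS and K10 among the baseline measures, to be repeated at follow-up under 7.2.2.

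**Urine outcome.** It is defined as "urine-confirmed abstinence from opioids in the last 4 weeks (longitudinal (weeks 4, 8, 12, and 24), binary". Baseline is therefore outside the outcome vector. For the other longitudinal outcomes, 8.3 does not say whether baseline is part of the vector.

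**The concern.** When a measure is taken both before randomisation and at follow-up, its baseline value is usually a good predictor of the follow-up value. Fixed adjustment for it is a standard way to gain precision from data already in hand. Here the baseline opioid urine result has no stated role: it is not an outcome time point, a named covariate, a moderator or a mediator. Baseline use of other substances appears, but only as binary moderators in exploratory models of the primary outcome.

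Entry timing makes some spread in baseline opioid status plausible. Section 5.2.1 allows consent 0-42 days after intake, while 4.1 and 7.2.1 schedule the research appointment at 7-21 days. The documents do not quantify that spread.

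Two things are at stake. One is precision on the secondary outcomes, including those on drug use. The other is reproducibility: with selection made outcome by outcome on trial data under an unstated rule, two analysts could follow 8.3 and fit different models.

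**Working it through.** **1. The plan's own figure.** Section 8.2 states "a sample size of 100 patients per treatment group (total N = 200", giving "sufficient power of 80% with a two-sided level of significance of 5" per cent, for "40% retained in TAU vs 59.7% retained in reSET-O + TAU".

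- Mean rate: (0.40 + 0.597)/2 = 0.4985.
- Pooled-variance formula: n = [1.960 × √(2 × 0.4985 × 0.5015) + 0.842 × √(0.40 × 0.60 + 0.597 × 0.403)]² / 0.197² ≈ 100 per arm, power 80.0%.
- Odds ratio: (0.597/0.403)/(0.40/0.60) = 2.22, which matches "This difference of 19.7% is equivalent to an odds-ratio of 2.22".

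The sizing reproduces. It concerns retention, which has no baseline value, so nothing below changes it.

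**2. Precision on a continuous secondary outcome.** Assumptions: 100 per arm, one follow-up, no missing data, and baseline-to-follow-up correlation r. The documents give no r, so a range is shown.

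- Unadjusted detectable difference at 80% power: (1.960 + 0.842) × √(2/100) = 0.396 SD.
- Adjusted variance: (1 − r²) times the unadjusted variance.
- Adjusted detectable difference: 0.396 × √(1 − r²).
- Power at 0.396 SD: Φ(2.802/√(1 − r²) − 1.960).
- Equivalent n per arm: 100/(1 − r²).

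| r | variance reduction | detectable difference (SD) | power at 0.396 SD | equivalent n per arm |
|---|---|---|---|---|
| 0.3 | 9% | 0.378 | 83.6% | 110 |
| 0.5 | 25% | 0.343 | 89.9% | 133 |
| 0.6 | 36% | 0.317 | 93.8% | 156 |

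The comparator is never adjusting for baseline. The stratification factors may already explain part of this variance, in which case the added gain is smaller.

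**3. Mean of four follow-ups.** Assume equal correlation r among all visits, a simplification of the planned autoregressive structure. The unadjusted variance is (1 + 3r)/4 and the adjusted variance is (1 + 3r)/4 − r².

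- r = 0.3: 0.475 to 0.385, a 19% fall.
- r = 0.5: 0.625 to 0.375, a 40% fall.

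**4. Would the plan's rule add the baseline value anyway?** Section 8.3 gives no threshold; take a two-sided 5% test as an assumption. With N = 200 and complete data, the test statistic for a correlation is t = r√198/√(1 − r²).

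- r = 0.3: 0.3 × √(198/0.91) = 4.4.
- r = 0.5: 0.5 × √(198/0.75) = 8.1.
- r = 0.6: 0.6 × √(198/0.64) = 10.6.

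All are well above 1.96. If the baseline value is tested, a rule of that kind would almost always select it at these correlations. The open question is whether it is tested, since 8.3 names no candidates.

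**5. Chance imbalance.** The standard error of the standardised baseline difference is √(2/100) = 0.14, so its 95% range is about ±1.96 × 0.14 = ±0.28 SD. At r = 0.5, an imbalance at that limit moves an unadjusted follow-up difference by 0.5 × 0.28 = 0.14 SD, about a third of 0.396. This is part of the sampling variation that the unadjusted interval already reflects.

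**6. Binary outcomes.** For urine-confirmed abstinence, and any other outcome with a logit link, adjustment changes the estimand to a conditional odds ratio. It can raise power but need not narrow the interval, so the r-squared figures do not carry over.

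**The case against.** The best reply is that 8.3 does provide for adjustment. A reader who stops at the three-variable sentence might infer that the models hold only treatment and strata and throw the baseline data away. The documents do not support that: the same paragraph and the general rule both commit to adding covariates related to the outcome. Step 4 strengthens the reply, because a strongly predictive baseline value would pass any ordinary threshold, and where it fails, little precision is lost. This stands as far as it goes. It does not settle whether the baseline value is a candidate, and it leaves the choice to outcome data.

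A reader might also infer that omitting baseline biases the treatment effect. It does not. Randomisation keeps the unadjusted comparison valid, and the cost is precision.

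A further objection is that, apart from urine, 8.3 does not exclude baseline from the outcome vector, and 7.2.1 says the K10 is collected at baseline and follow-up to address change over time. That is fair. For those outcomes the finding is that the handling is unstated, not that baseline is excluded.

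Finally, only the TLFB is expressly placed before randomisation at baseline. One paragraph of 7.2.1 puts the questionnaires before randomisation; a later one puts the surveys after assignment and app set-up. A scale completed after assignment is not a clean baseline covariate, so this objection conditions the fix.

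**Conclusion.** The point holds as a matter of pre-specification and efficiency for longitudinal secondary outcomes that have a baseline counterpart. Fixed adjustment for a value already collected is a better method than an undefined selection on outcome data.

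For one continuous follow-up, the gain over the plan lies between nothing, where the rule would have added the baseline value, and the full r-squared reduction, where that value would never have been considered: 9%, 25% or 36% at r of 0.3, 0.5 or 0.6. Every r is assumed, and the documents do not show where in that range the trial would fall. That baseline is the strongest predictor is plausible but undocumented.

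Weeks retained, treatment satisfaction (IAFF) and serious adverse events have no baseline counterpart and are unaffected. A reader might infer that the primary logistic model also needs baseline urine, or that N = 200 is in doubt. Neither follows: retention has no baseline value, nothing in the documents shows that baseline urine predicts it, and the stated sample size reproduces.

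**What to change.** In 8.3, Secondary outcomes, state that each longitudinal model includes, as a fixed term and whatever the observed association, the pre-randomisation value of the same measure where one exists:

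- baseline opioid urine result for urine-confirmed abstinence;
- baseline TLFB days for the two days-of-use outcomes;
- baseline CSS, SCS and K10 for those scales.

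This replaces outcome-driven selection for that term. State how a missing baseline value will be handled.

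Two passages must be reconciled first:

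- **Survey timing.** Section 7.2.1 must say once whether the baseline scales are completed before or after randomisation and app set-up.
- **Social functioning.** 8.3 lists EuroQol as an outcome and mediator, while 7.2.1 and the mediation paragraph of 8.3 name PROMIS. Its baseline term can be named once the instrument is settled.

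Cost: a short addition to 8.3, the two reconciliations, about one degree of freedom per model, and no new data. The primary model and sample size stay as they are.
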